#### **iv. Secondary Endpoints**

Secondary analysis will quantify the proportion of patients achieving minimal clinically significant changes in their tumors and comparing that to a theoretical expectation of 5% improvement with a Fisher exact test, and the effect of the *PTCH1* mutation on tumor volume reduction will be assessed with an independent samples t-test. These analyses will use the same population as the primary endpoint.

All analyses will be done using IBM SPSS Version 21.

v. Sample size determination. Twenty subjects will be recruited. Analysis of the primary endpoint is capable of detecting changes in tumor volume in the Wilcoxon tests of approximately 1.0 and .68 SD, assuming a 2-tailed type 1 error of 5% and power of 80% and then assuming either n=10 (separate analysis of the NBCSS-associated and sporadic cohorts) or n=20 (combined analysis of both cohorts), respectively (G\*Power, v3.1).

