## 3. STUDY DESIGN

### 3.1 Description of the Study

This is a single-center, interventional, single-arm, open-label, two-cohort clinical trial. A total of 40 patients will be screened in order for 20 patients to be enrolled (10 with NBCCS-associated KCOT and 10 with sporadic KCOT) over a period of 2 years. This is a 3 year study where each patient will undergo up to 1 year of treatment and up to 2 years of post-treatment follow-up. If a patient is experiencing an ongoing adverse event at the time of the study completion, he/she will be followed-up until resolution of the adverse event or until the condition has stabilized. The same applies to patients who are withdrawn from the study due to adverse events.

It is estimated that it will take approximately 2 years to recruit 20 patients for the study (10 with NBCCS-associated KCOT and 10 with sporadic KCOT).

All patients will be assessed for safety and efficacy of the study drug GDC-0449 (Vismodegib).

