## **4.2 Study Treatment**

This is a single-center, interventional, single-arm, phase II, open-label, two-cohort clinical trial. A total of 40 patients will be screened in order for 20 patients to be enrolled (10 with NBCCS-associated KCOT and 10 with sporadic KCOT) over a period of 2 years. Only patients with a diagnosis of recurrent (maxillary or mandibular) sporadic KCOT or NBCCS-associated KCOT (single or multiple) will be recruited. All patients will receive 150 mg/day of GDC-0449 (Vismodegib) orally for 1 year. All patients will be assessed for safety and efficacy of the study drug GDC-0449 (Vismodegib).

This is a 3 year study where each patient will undergo up to 1 year of treatment and up to 2 years of post-treatment follow-up.

The Sponsor Investigator of the study will ensure maintenance of complete and accurate records of the receipt, dispensation, and disposal or return of all Vismodegib in accordance with 21 Code of Federal Regulations (C.F.R.), Part 312.57 and 312.62 and Genentech requirements.

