### **Panoramic Radiograph and Volumetric CT Scan**

Tumor volume will be measured at baseline, and tumor response (reduction in tumor volume and recurrence) will be measured during the treatment phase and post-treatment phase by Panoramic Radiograph and Volumetric CT scan. The use of Panoramic Radiograph and Volumetric CT scan to measure the tumor volume are obtained for clinical assessment purposes only. No additional scans will be performed for research purposes. Disease progression during the treatment phase will be classified by an increase of at least 20%, with an absolute change greater than 5 mm in tumor size after 3 months of treatment. KCOTs grow within the bone. CT scan and panoramic radiograph are superior, with regard to sensitivity and specificity, in terms of evaluating bone involvement.

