### **b. Efficacy Analysis**

#### **i. Primary Endpoint**

The effect of GDC-0449 will be evaluated (at a significance level of 5% and controlling the false discovery rate) using Wilcoxon signed rank tests to compare the mean KCOT volume at baseline to those acquired at 6, 12, 24,36 and 48 months. These comparisons will also be accomplished using paired t-tests.

ii. Subject population for this analysis. As a primary intention to treat (ITT) analysis, we will analyze data from all randomized subjects who complete Phase 1. For these analyses, Phase 1 values will be substituted for missing observations. Should more than 20% of the data be missing at any observation interval, analysis of that interval will be abandoned. Deviations from this plan, for example, emergent interest in the analysis of the all-treated or protocol-compliant subjects, will be transparently pursued and reported.

iii. Treatment of missing data. Two secondary effectiveness analyses will either carry the last observation forward into missing cells, or use maximum likelihood estimates of those values. We expect the best estimate of efficacy is likely to lie within the limits set by these conservative (ITT) and liberal (LOCF, ML) treatments of missing data.

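### The secondary responder analysis applies Fisher's exact test to one sample against a fixed 5%; an exact one-sample binomial test is needed

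*Combined protocol and SAP*

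**What the plan says.** Section 4.8, b.iv (Secondary Endpoints) sets out a responder analysis. It will quantify the "proportion of patients achieving minimal clinically significant changes in their tumors", "comparing that to a theoretical expectation of 5% improvement with a Fisher exact test". On the population it adds: "These analyses will use the same population as the primary endpoint". The primary population rule in b.ii keeps patients with missing scans in the analysis: "For these analyses, Phase 1 values will be substituted for missing observations". The denominator can therefore be as large as the full sample, for which b.v says "Twenty subjects will be recruited", ten in each cohort.

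There is no control group. Section 3.1 describes a "single-center, interventional, single-arm, open-label, two-cohort clinical trial", and section 4.2 repeats this: "This is a single-center, interventional, single-arm, phase II, open-label, two-cohort clinical trial".

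The plan gives no comparison counts and no comparator size. For this test it also gives no alpha, sidedness or visit, and it does not say whether the cohorts are pooled. It sets no threshold for a response. The nearest definition, in section 4.4 under Panoramic Radiograph and Volumetric CT Scan, concerns growth only: "Disease progression during the treatment phase will be classified by an increase of at least 20" per cent, together with an absolute change.

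**The concern.** Fisher's exact test works on a 2x2 table with two rows of observed counts. Here one row is observed (responders and non-responders among the treated patients) and the other is a theoretical constant. A constant has no denominator, so the test cannot be run until someone makes up a group whose proportion is 5%. Fisher then treats that group as real data with its own sampling error, which a fixed value does not have.

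The size of that group is a free choice, and it would be made when the data are already in hand. If it changes the p-value materially, the same data can be reported as significant or not at the analyst's discretion. If the group is small, most of the test's power is lost. This is the plan's only efficacy analysis of how many patients benefit, so the loss would matter in a trial of 20.

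**Working it through.** **The plan's own figures.** The plan states no operating figure for the responder test. Its only power statement (b.v) concerns the primary Wilcoxon tests: detectable changes of about 1.0 SD at n=10 and 0.68 SD at n=20. Noncentral-t power with n scaled by the Wilcoxon efficiency 3/π gives 1.026 and 0.678 SD. Those figures reproduce and are not at issue.

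**Inputs**
- n = 20 (b.v), both cohorts combined (assumption).
- Reference rate 0.05 (b.iv), read as 5% of patients. This is the only reading that fits a test of proportions.
- Two-sided 5% level, carried over from the primary endpoint (assumption).
- Size m of the comparison group: not in the plan. Groups from 1/20 to 50/1000, each at exactly 5%, are tried.

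**Exact one-sample binomial test.** p(r) = P(X ≥ r), where X ~ Bin(20, 0.05).
- P(X = 0, 1, 2, 3) = 0.35849, 0.37735, 0.18868, 0.05958.
- r = 3: 1 − (0.35849 + 0.37735 + 0.18868) = 0.0755, not significant.
- r = 4: 1 − 0.98410 = 0.0159, significant.

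The two-sided p-value by the minimum-likelihood method is the same at both counts. Doubling the tail gives 0.0318 at r = 4, so the conclusion does not change. The Clopper-Pearson 95% interval is 3.2% to 37.9% at 3/20 and 5.7% to 43.7% at 4/20, so its lower limit first passes 5% at 4 responders.

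**Fisher's test with an invented row c/m.** With t = r + c total responders, each table has probability C(20, x)·C(m, t − x) / C(20 + m, t). The two-sided p-value sums all tables no more probable than the one observed.

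| Notional group | p at 4/20 | Smallest significant count | p at that count |
|---|---|---|---|
| 1/20 | 0.342 | 7 | 0.044 |
| 2/40 | 0.089 | 5 | 0.036 |
| 3/60 | 0.062 | 5 | 0.021 |
| 4/80 | 0.049 | 4 | 0.049 |
| 5/100 | 0.041 | 4 | 0.041 |
| 50/1000 | 0.018 | 4 | 0.018 |
| Exact binomial | 0.016 | 4 | 0.016 |

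Against 1/20, 6 responders give p=0.092 two-sided and 0.046 one-sided, so a one-sided test would need 6. As m grows, Fisher converges on the binomial: 5000/100000 gives 0.0159 at 4/20.

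**What the required count costs.** P(X ≥ k) for n = 20:

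| Required count k | True rate 5% (type I error) | True rate 30% | True rate 40% |
|---|---|---|---|
| 4 | 0.0159 | 89% | 98% |
| 5 | 0.0026 | 76% | 95% |
| 6 | 0.0003 | 58% | 87% |
| 7 | 0.00003 | 39% | 75% |

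In every case checked Fisher is at most as sensitive as the binomial test, and the binomial rule already keeps its error at 1.6%, well inside 5%.

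**By cohort (n = 10).** The binomial test needs 3 responders (p=0.0115; 2/10 gives 0.086). Two-sided Fisher needs 4 against 1/20 and 3 against 2/40 or larger.

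**The case against.** The best defence is that the practical reach is narrow. Within the groups in the table, the choice changes the verdict only if 4, 5 or 6 of 20 respond, and for groups of 80 or more the required count is the same as for the binomial. Section 1.2 expects activity similar to that in basal cell carcinoma, where the protocol's tables show response rates from 30% (metastatic, independent review) to 60% (locally advanced, investigator). The chance of landing on 4 to 6 responders is 50% at a true rate of 30%, 23% at 40%, 16% at 43% and 0.6% at 60%. Even a required count of 7 has 83% power at 43%. This stands as a limit on size: the loss is serious only toward the low end of that range. It does not settle the matter, because those rates rest on other response definitions and the response in this trial is undefined.

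A second defence is that the author meant an exact binomial test and misnamed it. If so, the name still needs correcting, since an analyst who follows the text would run something else.

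A third is that alpha and sidedness can be carried over from the primary endpoint. That is a natural reading, and the figures above adopt it, so those gaps are minor beside the missing comparator.

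Two further cautions are fair. The range of 4 to 7 is not a bound: a group of 10 cannot hold exactly 5%, and 0/10 or 1/10 would require 8 or 10 responders. Also, changing the test does not supply the missing responder threshold, without which neither test can be run.

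**Conclusion.** The concern holds. Fisher's exact test is the wrong procedure for one observed proportion against a fixed value, and it cannot be carried out from the plan as written. For n=20 combined, a two-sided 5% level, 5% read as a responder rate, and notional groups of 20 to 1000 set at exactly 5%, the required count runs from 7 to 4 depending only on an unstated choice. The exact binomial test requires 4.

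The error is conservative: it risks a missed responder signal or an analyst-chosen p-value, not an inflated false-positive rate. The analysis is secondary, no success rule hangs on it, and the primary Wilcoxon comparison is untouched. It should be corrected, but it does not threaten the trial's main conclusion.

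**What to change.** In section 4.8, b.iv, replace Fisher's test with an exact one-sample binomial test of the responder proportion against 0.05 in the combined group, reported with a Clopper-Pearson 95% confidence interval. In the same place:

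- State alpha and sidedness, and name the two-sided method if the test is two-sided.
- State the visit tested.
- Define the volume change that counts as a response.
- Confirm that the 5% means 5% of patients reaching that change.
- If each cohort of 10 is also to be tested, which the plan does not say, use the same binomial test.

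This takes a few sentences and no new data, visits or patients. The one item that needs outside input is the responder definition, a clinical decision to be made before the data are analysed.

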# 1. INTRODUCTION

## 1.1 Disease

## Background

The keratocystic odontogenic tumor (KCOT) is a benign odontogenic neoplasm that has destructive and infiltrative behavior [1]. KCOT can occur as part of nevoid basal cell carcinoma syndrome (NBCCS) or as a sporadic case. KCOTs are the most prominent feature of NBCCS and they are present in 65-100% of cases [2]. Four to five percent of KCOT patients have NBCCS [3]. Although KCOTs are benign, they tend to be aggressive, with local invasion of bony structures, extensive growth, and potential for substantial disfigurement [4]. This condition has a high recurrence rate and it is estimated that after initial treatment with various procedures recurrence ranges from 2.5% to 62.5% [5]; [6]. The only therapeutic option for patients affected by KCOT is surgery which can involve significant destruction of tissue; often multiple surgeries are required. Thus, the management of patients with KCOT has challenged and frustrated both patients and providers [6].

Research findings suggest that mutations in *PTCH1* are frequent in both sporadic KCOT (29%) and NBCCS-associated KCOT (approximately 88%). Thus *PTCH1* gene mutations may play a significant role in the pathogenesis of NBCCS and the related sporadic tumors [7]. In this study, we plan to test GDC-0449 (Vismodegib) as novel treatment in two groups of patients: NBCCS-associated KCOT and sporadic KCOT cohort. The inclusion of this two-group cohort is based on the evidence that mutations of the hedgehog (Hh) pathway are present in both groups and consequently all patients affected by KCOT may benefit from a systemic Hh pathway antagonist.

We hypothesize that an inhibitor of the sonic Hh can be an important therapeutic advancement in the treatment of KCOT. This study proposes to test GDC-0449 (Vismodegib) for treating patients with KCOT. This drug has the potential to reverse KCOT proliferation. GDC-0449 may be useful as a neo-adjuvant prior to surgery in patients with KCOT or may be a surgery substitute in some cases. The use of GDC-0449 prior to surgery may lead to tumor shrinkage and reduce the extent of required surgery or eliminate the need for surgery completely.

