## 2.2 Secondary Objectives

The secondary objectives of the study are:

- a. To determine the time of response of a GDC-0449 anti-proliferative effect (i.e. tumor shrinkage) after administration of the drug up to one year or until treatment is stopped;
- b. To assay germ line *PTCH1* mutations before treatment with GDC-0449 in patients with NBCCS-associated KCOT;

If tumor removal is required, to assess tumor *PTCH1* mutations before and after treatment with GDC-0449 in NBCCS-associated KCOT and sporadic KCOT in order to determine the correlation of tumor response and the presence of tumor *PTCH1* mutation.

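### The PTCH1 comparison uses an unadjusted two-sample t-test although mutation status is tied to cohort, so about 61% of any NBCCS-versus-sporadic difference in response would appear as a PTCH1 effect

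*Combined protocol and SAP*

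**What the plan says.** Section 4.8(b)(iv) states that the effect of the PTCH1 "mutation on tumor volume reduction will be assessed with an independent samples t-test". It adds: "These analyses will use the same population as the primary endpoint". No covariate, stratum or cohort split is named for this test. Separate analysis of the two cohorts is mentioned only in the sample-size paragraph, for the primary endpoint.

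Section 1.1 reports that PTCH1 mutations "are frequent in both sporadic KCOT (29%) and NBCCS-associated KCOT (approximately 88" percent). Section 3.1 plans for "20 patients to be enrolled (10 with NBCCS-associated KCOT and 10 with sporadic KCOT").

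Section 2.2 has two PTCH1 objectives. One is to assay germ-line "mutations before treatment with GDC-0449 in patients with NBCCS-associated KCOT". The other is to relate tumor response to tumor PTCH1 mutation in both cohorts, when tumor removal is required. Section 4.8 does not say which of the two, germline or tumor status, forms the groups in the t-test. Appendix C lists a PTCH1 mutation in normal tissue among the major diagnostic criteria for the syndrome.

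**The concern.** A two-sample t-test attributes the whole difference between mutated and unmutated patients to the mutation. Here those groups also differ sharply in syndrome status. If NBCCS and sporadic tumors respond differently for any other reason, part of that difference is reported as a PTCH1 effect; if the other reason works the opposite way, a real PTCH1 effect can be cancelled. Relating response to PTCH1 is a stated secondary objective, and Section 1.1 justifies enrolling both cohorts by the presence of Hedgehog-pathway mutations in each. The test as written cannot separate mutation from syndrome on the question it is meant to answer.

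**Working it through.** **The plan's own figure.** The only stated precision is for the primary Wilcoxon test: "approximately 1.0 and .68 SD" for n=10 and n=20, "assuming a 2-tailed type 1 error of 5% and power of 80" percent. A one-sample noncentral t with effective size n × 3/π gives 1.03 SD and 0.68 SD, and simulated exact signed-rank power at the stated effects is 78.5% and 80.2%. The figure reproduces, but it concerns change from baseline. No power is stated for the PTCH1 comparison.

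**Inputs.** Mutation rates 0.88 and 0.29 (Section 1.1, read as tumor rates); 10 patients per cohort (Section 3.1). Assumptions: all 20 patients typed, within-cohort SD of 1, normal data.

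**Make-up of the two groups.**
- Mutated: 10 × 0.88 + 10 × 0.29 = 8.8 + 2.9 = 11.7, of whom 8.8/11.7 = 75.2% are NBCCS.
- Unmutated: 1.2 + 7.1 = 8.3, of whom 1.2/8.3 = 14.5% are NBCCS.
- Correlation: phi = (8.8 × 7.1 − 1.2 × 2.9) / √(10 × 10 × 11.7 × 8.3) = 59.0/98.5 = 0.60.

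**Share of a cohort difference passed to PTCH1.** With no PTCH1 effect and a cohort difference Δ, the expected t-test contrast is Δ × (0.752 − 0.145) = 0.61Δ. Under other assumed rates (NBCCS/sporadic) the share is 0.41 (70%/29%), 0.44 (88%/50%) and 0.78 (100%/29%).

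**Error rates.** Simulation with 20,000 trials per setting and no PTCH1 effect. Δ is not in the documents, so the range is assumed.

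| Assumed Δ (SD) | t-test rejects | Model with PTCH1 and cohort rejects |
|---|---|---|
| 0 | 5% | 5% |
| 0.5 | 10% | 5% |
| 1.0 | 22% | 5% |
| 1.5 | 39% | 5% |

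If only 5 + 5 patients were typed (assumption), the t-test would reject in about 13% at Δ = 1.0 SD.

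**Masking.** For a true PTCH1 effect of 1 SD, t-test power is about 54% when the cohorts do not otherwise differ, and about 10% when an opposing 1 SD cohort difference is present. The adjusted model has about 35% in both cases.

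**Cost of adjustment.**
- Expected information without cohort: 20 × 0.585 × 0.415 = 4.86.
- Expected information within cohorts: 9 × 0.88 × 0.12 + 9 × 0.29 × 0.71 = 0.95 + 1.85 = 2.80, or 58% of 4.86. The standard error at these expected values rises by √(4.86/2.80) = 1.32.
- Averaged over the mutation splits that can occur, the rise is about 35%. A variance inflation factor from phi alone, 1/(1 − 0.599²) = 1.56, would give only √1.56 = 1.25, because it ignores that variation.
- Power for a true 1.3 SD effect falls from about 76% to 53%. The effect detectable with 80% power rises from about 1.34 to 1.78 SD.
- Expected unmutated NBCCS patients: 10 × 0.12 = 1.2. The chance of none is 0.88^10 = 28%; the chance of at most one is 0.88^10 + 10 × 0.12 × 0.88^9 = 66%. The sporadic cohort, about 3 mutated versus 7 unmutated, supplies 1.85/2.80 = 66% of the information.

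**The case against.** The strongest reply is that the plan never says which PTCH1 variable is tested. Section 2.2 limits the germline objective to NBCCS patients; a germline test confined to that cohort could not be confounded by cohort. That is true of that reading, but the correlation objective in the same section names tumor PTCH1 in both cohorts, and neither Section 4.4.2 nor Appendix A limits blood testing to NBCCS patients. The ambiguity stands and belongs in the fix.

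The typed number is also uncertain. Tumor status depends on excision or biopsy tissue, although Section 4.4 allows stored paraffin-embedded samples as a fallback. The error rates above for 20 patients are therefore conditional on full typing.

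A reader might infer that the test will often declare a PTCH1 effect that does not exist. The documents do not support that. They give no response difference between cohorts; at zero there is no bias, and at 0.5 SD the error is about 10%. A reader might also suppose that NBCCS patients, who can have several KCOTs, have larger volumes and larger raw reductions. That is a possible mechanism only: no volumes by cohort are given, and nothing says that volumes are summed across lesions.

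Finally, adjustment is weak with so few unmutated NBCCS patients, and for germline status it could remove part of the effect sought, because the mutation helps define the syndrome. Both points hold. They argue for an exploratory label and for keeping any germline analysis inside the NBCCS cohort, not for leaving the pooled comparison unadjusted.

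**Conclusion.** The concern holds in a bounded form. On the natural reading, a pooled t-test, about 61% of any cohort difference is expected to be attributed to PTCH1 at the protocol's own rates. It would be too strong to say that all of it is. The size of the resulting error rests on a cohort difference that the documents do not give and on all 20 patients being typed. Separate t-tests within each cohort would avoid the problem, but the plan does not specify them. The point concerns one secondary test with no stated power; neither the primary efficacy comparison nor the safety analysis is affected.

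**What to change.** In Section 4.8(b)(iv):

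- Define the grouping variable as tumor PTCH1 status, matching the correlation objective in Section 2.2.
- Replace the t-test with a linear model of volume reduction on PTCH1 status and cohort.
- Report the adjusted PTCH1 difference with its 95% CI, and the mutated and unmutated counts and the estimates within each cohort.
- Label the result exploratory.
- Confine any germline analysis to the NBCCS cohort, because germline PTCH1 is itself a diagnostic criterion in Appendix C.

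This changes wording only. Cohort is known for every patient, and no visit, assay or patient is added. The price is the loss of precision shown above, with an adjusted estimate that rests mainly on the sporadic patients. If no unmutated NBCCS patient is enrolled, it rests on them entirely, and the report should say so.

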## **4. MATERIALS AND METHODS**

### **4.1 Subject Selection**

#### **4.1.1 Inclusion Criteria**

Patients are eligible to participate in the study if they meet the following criteria:

- Males and females, 18 years of age and above at the time the informed consent form is signed;
- Able to understand and sign the Informed Consent Form and other necessary paperwork prior to initiation of study procedures;
- Able to communicate with the investigator/study site personnel, understand and comply with the study requirements, and willing to return for specified visits at the appointed time;
- Patients who have received prior treatment for their KCOT and with a diagnosis of recurrent (maxillary or mandibular) sporadic KCOT or NBCCS-associated KCOT (single or multiple);
- Diagnosis of KCOT will be done by past pathology report or by biopsy at the study site, if applicable;
- Willingness to consent to biopsy of the lesion, if needed;
- Willingness to delay excision of the target tumor site, unless evidence of disease progression or lack of drug tolerability;
- For female patients of childbearing potential, agreement to use two acceptable methods of birth control, including one barrier method during the study and 24 months after discontinuation of study drug;
- For males with female partners of childbearing potential, agreement to use a male condom (with spermicide) and to advise their female partners to use an acceptable method of birth control during the study and for 3 months after the discontinuation of the study drug;
- Agreement not to donate blood/blood products during the study and for 24 months after the discontinuation of the study drug;
- For males not to donate sperm products or semen during treatment and for 3 months after the discontinuation of the study drug;
- Able and willing to swallow pill;

- No malabsorption syndrome or other condition that would interfere with enteral absorption;
- At least 4 weeks since last chemotherapy, investigational therapy, radiotherapy or major surgical procedure and recovered from the first study drug administration;
- KCOT measures at least 1 cm in one dimension on pretreatment volumetric CT scan;
- No clinically significant abnormalities with clinical laboratory assessments;

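### The PTCH1 t-test leaves tumor volume reduction undefined as absolute or percent and takes no account of baseline volume, so it can show a false PTCH1 effect or hide a real one if the groups start at different sizes

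*Combined protocol and SAP*

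**What the plan says.** Section 4.8 b.iv (Secondary Endpoints) states that the effect of the PTCH1 "mutation on tumor volume reduction will be assessed with an independent samples t-test". On the analysis set it adds: "These analyses will use the same population as the primary endpoint". No covariate, stratification or baseline adjustment is named for this test anywhere in Section 4.8. Baseline KCOT severity appears only in the retention analysis (4.8 a). Reduction is not defined as absolute or percent.

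The data needed for adjustment are collected. Section 4.4 (Panoramic Radiograph and Volumetric CT Scan) says: "Tumor volume will be measured at baseline, and tumor response (reduction in tumor volume and recurrence) will be measured during the treatment phase". Section 4.4.2 and Appendix A schedule the volumetric CT at baseline. Section 4.1.1 sets a lower limit on size, "KCOT measures at least 1 cm in one dimension on pretreatment volumetric CT scan", and no upper limit.

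On sample size the plan says "Twenty subjects will be recruited". It gives power for the primary Wilcoxon tests only, not for the PTCH1 comparison.

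**The concern.** At the same fractional response, a large tumor loses more volume than a small one. If both groups shrink by 50% and one starts at volume V and the other at 2V, the absolute reductions are 0.5V and 1.0V, although the drug has done the same in each. The reverse also happens. If mutated tumors shrink by 65% from 0.5V and non-mutated tumors by 30% from V, the reductions are 0.325V and 0.30V, and a large difference in response nearly vanishes.

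Nothing in the design balances starting volume between genotype groups. This t-test is the only formal test specified for the Section 2.2 aim of relating tumor response to PTCH1 mutation. With the scale left open, it could also be chosen after the data are seen.

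**Working it through.** **1. The plan's own figure.** Section 4.8 b.v claims that the primary analysis is capable of "detecting changes in tumor volume in the Wilcoxon tests of approximately 1.0 and .68 SD" for "n=10 (separate analysis of the NBCSS-associated and sporadic cohorts) or n=20 (combined analysis of both cohorts"), at 80% power and two-sided 5%. Noncentral-t power with n multiplied by the Wilcoxon relative efficiency 3/π gives 1.026 SD at n=10 and 0.678 SD at n=20. The stated figures reproduce, but they do not describe the two-group PTCH1 test.

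**2. Likely group sizes.** Section 1.1 gives PTCH1 mutation in about 88% of NBCCS-associated and 29% of sporadic KCOT. With 10 patients per cohort, 8.8 + 2.9 = 11.7 mutated, so about 12 against 8. At that split an unadjusted two-sided 5% t-test needs a difference of 1.35 SD for 80% power, and has 54.5% power at 1.0 SD.

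**3. Simulation.** None of these assumptions is in the documents:
- 12 mutated and 8 non-mutated patients, no missing data
- log-normal baseline volume V0 with log-SD 0.5, 0.8 or 1.0
- V1 = V0 × exp(N(μ, 0.4)), with μ = log(1 − shrinkage) for the group

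The table gives the percent of trials with p < 0.05. Three values in a cell are for log-SD 0.5 / 0.8 / 1.0. Repeat runs agree to within about two percentage points.

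| Setting | Absolute, t-test | Absolute, adjusted for V0 | Percent, t-test | Percent, adjusted for log V0 |
|---|---|---|---|---|
| No effect (50% both), equal baselines | about 4 | at most 6 | 4-6 | 4-6 |
| No effect, baselines differ twofold | 36 / 16 / 10 | at most 6 | 4-6 | 4-6 |
| No effect, baselines differ threefold | 70 / 36 / 20 | at most 6 | 4-6 | 4-6 |
| 65% vs 30% shrinkage, equal baselines | 61 / 33 / 22 | 87 / 77 / 68 | 94 | 92-93 |
| 65% vs 30%, mutated tumors half the size | 11 / 8 / 7 | 57-60 | 94 | 78-89 |

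**4. A second shrinkage model.** With 40% mean shrinkage in both groups (SD 25 percentage points), false positives for the absolute t-test are 26.7 / 12.5 / 7.8% at twofold and 54.9 / 28.0 / 16.4% at threefold. The unadjusted percent t-test stays at 4.8-5.3%. The pattern is the same and the sizes are smaller.

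**5. When the covariate matters on the percent scale.** If fractional shrinkage itself depends on tumor size (assumed slope of 0.2 of the log volume ratio on log V0) and baselines differ, the unadjusted percent t-test has 8-16% false positives. The model with log V0 stays at 4-5%.

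**6. Precision without the proportional model.** With equal SDs and pre/post correlation ρ, the variance of the adjusted estimate relative to the change score is (1+ρ)/2. At ρ = 0.5 this is 0.75, and power at 1.0 SD rises from 54.5% to 66.5%. At ρ = 0.3, 0.7 and 0.9 it rises to 72.6%, 61.1% and 56.4%. The documents do not give ρ.

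**The case against.** The strongest reply is that the harm comes from an undefined scale rather than a missing covariate. This largely stands. Under proportional shrinkage a plain t-test on percent reduction keeps 4-6% false positives and has 94% power, with no covariate. In that model the covariate only costs power: at a twofold difference in either direction, power falls from about 94% to 78-89%, because baseline volume and PTCH1 status are then correlated. The covariate earns its place only if fractional response varies with size (step 5), which the documents neither show nor exclude.

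Three further points stand:
- The documents give no baseline volume distribution and no link between PTCH1 status and tumor size. The imbalance is a possibility.
- The 12/8 split is inferred. Section 2.2 makes tumor PTCH1 assessment conditional on tumor removal, so fewer than 20 patients may be analysable.
- The imbalance that the documents do show is by cohort (88% against 29%). Adjusting for baseline volume does not deal with it.

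The reply does not show that percent was intended. Section 4.8 b.i compares mean volumes, and the sample size statement speaks of changes in tumor volume, so the absolute reading is at least as natural.

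**Conclusion.** The point holds in conditional form. The plan should say what reduction means and should use the baseline volume it already collects. If reduction is absolute and the groups start at different sizes, a nominal 5% test can be positive in about 10-36% of trials at a twofold ratio and 20-70% at threefold with no PTCH1 effect, and a real effect can be masked. These figures rest on the assumptions in step 3.

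A reader might infer two stronger claims that the documents do not support.
- *That the test will show a false or hidden effect.* This needs both a baseline imbalance and the absolute scale. The documents establish neither.
- *That most of the power is lost for want of adjustment.* In the simulation with equal baselines, 61% against 92-93% is a loss of about a third. Only the more skewed volumes (33% and 22%) lose more than half, and that gain comes from the percent scale, since the plain percent t-test already has 94%. In step 6, at ρ = 0.5, the loss is (66.5 − 54.5)/66.5 = 18%. The small sample is itself a main limit, with 1.35 SD needed for 80% power.

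**What to change.** In Section 4.8 b.iv:
- Define reduction as percent change in KCOT volume from baseline. This keeps fully resolved tumors (volume 0) in the analysis.
- Replace the t-test with a linear model of percent change on PTCH1 status, with log baseline KCOT volume as covariate, alongside any cohort term adopted.
- Report the adjusted PTCH1 difference with its 95% CI.
- Show the unadjusted percent-change comparison as a sensitivity analysis.
- Tabulate baseline volume by PTCH1 status.

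The change is to wording only. It uses the scheduled CT scans and can be run in SPSS, the package that the plan names. The statistical cost is one degree of freedom out of 18, plus the loss of precision described above when baseline volume and PTCH1 status are correlated. Confounding of PTCH1 status with cohort needs its own remedy.
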